**Describe the different populations that will be recruited and enrolled**

---

*Provide the inclusion/exclusion criteria for each population.*

Loneliness is a serious public health problem that affects more than 35% of older adults. Given that the study is testing an intervention to reduce loneliness and its implications among older adults, we will only include **adults 50 years of age or older**. We will be recruiting adults aged 50 and older living in Southern Nevada.

**Inclusion criteria:** *adults age 50 years or older living in Southern Nevada*

**Exclusion criteria:** *cognitive or language barriers that would be determined by whether they are able to understand and repeat information from informed consent. If we determine they are not able to provide informed consent, they will be excluded from the study.*

\*required

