**Include sample size calculations, if applicable.**

Adults age 50 years or older, who are willing to participate will be recruited unless they have a significant cognitive or language barrier that will prevent them from successfully answering the study questionnaires.

We will use a randomized controlled trial (RCT) with waitlist control to determine the intervention's feasibility, acceptability, and initial efficacy. Although the proposed study is a feasibility pilot study, we will investigate the preliminary efficacy of the intervention. Therefore, the sample size for this current pilot study was estimated based on four repeated measurements: (baseline, right after intervention, post-intervention (at one month), and follow-up (at second month). Using an estimated effect size (Cohen's  $f= 0.2$ ), an alpha of 0.05, and a power of 90%, for a repeated measure ANOVA between-within effects, with two groups and four measurement time points, the sample size was determined to be 46. This sample size was then increased by 33% to allow for attrition, to give the total sample of 60. The sample size was determined using G\*Power (v. 3.1.9.7).

**Given the interest from the community, we are increasing our sample size to 100. We do not want to exclude eligible community members who might benefit from participating in the study. This will help increase the study power as well.**

\*required

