## **Purpose**

---

*State the purpose of the study in lay terms.*

**Note:** DO NOT copy and paste directly from your grant proposal, dissertation prospectus, clinical protocol, etc.

The purpose of the study is to examine whether the intervention (Loving kindness meditation) is feasible and acceptable among adults 50 years or older. The second aim is to examine the preliminary efficacy or impact of the intervention on reducing loneliness, depressive symptoms, and anxiety and improving compassionate love and cognitive function among this population group.

\*required

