## **Objectives**

---

*Briefly describe your research questions and the objectives of this study in lay terms. State what you hope to learn from the study and assess the importance of this new knowledge. What do you aim to achieve through this research?*

**Note:** DO NOT copy and paste directly from your grant proposal, dissertation prospectus, clinical protocol, etc.

Objective 1: To evaluate the feasibility of implementing loving-kindness meditation (LKM) among older adults. Research Question 1: Is LKM intervention feasible and acceptable among older adults? We hope to find that intervention is feasible and acceptable among this population. We will also gather data on challenges and how to improve/refine this intervention for future research through a focus group interview.

Objective 2: To examine the preliminary effectiveness of the LKM in increasing positive emotions such as compassionate love. Research Question 2: What is the preliminary effect of the LKM on compassionate love? Hypothesis: Older adults will show an increased compassionate love (Self-compassion scale) after 30 days of intervention. Objective 3: To examine the preliminary impact of the LKM in reducing loneliness and improvement in cognitive function and mental health. Research Question 3: What is the preliminary effect of the LKM on loneliness, depressive symptoms, anxiety scores, and cognitive function?

Hypothesis: Older adults will show a reduced feeling of loneliness, depressive symptoms (CESD) and anxiety (PROMIS anxiety scale), and improved cognitive function (PROMIS cognitive function scale) after 30 days of intervention.

\*required

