The orientation is about 10-20 minutes (with both in person and recording) and recorded LKM training is about 30-35 minutes (video links provided under interview section as attachments). We will also have a Questions and Answers session, which could take up 10-20 minutes. Participants will be then given the link to fill out the post intervention questionnaires on their own and if they request paper and pen version, those would be available as well.

After 3 weeks of intervention, we will call to set up an appointment to meet both intervention and control group to collect data for 4 week data collection. At this data collection session, we will also collect 30-day journal folders. At this time, we will also ask for **8-10** volunteers for focus group study (we will have two group of 4-5 participants) and once we have their permission, we will set up another appointment for focus group interview, which may take up to 90 minutes at either OLLI campus or apartment's media room. We will also set up an appointment for control group for their LKM training after collecting time 2 data from them. We will do a month follow-up again at 8 week for intervention group and 4week post-intervention data collection for control group.

There are three areas of outcome measures we are aiming to determine: feasibility, acceptability, and initial efficacy:

(1) feasibility of collecting measures of self-compassion, loneliness, depressive symptoms, anxiety, and cognitive function; (2) acceptability of the intervention (i.e., satisfaction, adherence, recruitment, and retention rates); and (3) initial efficacy (i.e., changes in loneliness along with self-compassion, depressive symptoms, anxiety and cognitive function at immediately post-intervention, at 30 and 60 day follow-up). We will evaluate feasibility through participants' satisfaction, their continued use of intervention after the study completion, how appropriate the intervention was for them, their positive or negative effects associated with the intervention. We will also assess their active and continual participation, retention rates, participation rate, and missing data on collected measures. We will also conduct two focus group with **4-5 participants in each group** at the end of the study to determine the feasibility of the study and how we can further improve the intervention for future research. PI will transcribe the qualitative interviews.

\*required

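### The only powered efficacy test is a four-time ANOVA that does not isolate the hypothesised 30-day effect; a baseline-adjusted week-4 comparison of one named outcome would

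*Combined protocol and SAP*

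**What the plan says.** The Objectives section sets two efficacy hypotheses. Objective 2 has its own: "Older adults will show an increased compassionate love (Self-compassion scale) after 30 days of intervention". Objective 3 groups the rest: "Older adults will show a reduced feeling of loneliness, depressive symptoms (CESD) and anxiety (PROMIS anxiety scale), and improved cognitive function", again after 30 days. In the outcome paragraph under How will you conduct this study?, initial efficacy is described as "changes in loneliness along with self-compassion, depressive symptoms, anxiety and cognitive function at immediately post-intervention, at 30 and 60 day follow-up".

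The sample size section is the only place with an error rate. It uses "an alpha of 0.05, and a power of 90" per cent, "for a repeated measure ANOVA between-within effects, with two groups and four measurement time points, the sample size was determined to be 46". The four times are baseline, right after the intervention, one month and second month. The effect size is f = 0.2 and no outcome is attached to it. The 46 became 60 for attrition and has since been raised to 100, with only the remark that this helps power.

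The procedures section gives controls one additional collection, at week 4, before their own training. They are then trained, and week 8 serves as their 4-week post-intervention visit. The Compensation section goes further. It pays controls for baseline, time 2, the training session, a post-intervention visit and then a one-month follow-up.

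On which outcome leads, the text points two ways. The Purpose section says "The second aim is to examine the preliminary efficacy or impact of the intervention on reducing loneliness" and then lists the others, and the population section says "the study is testing an intervention to reduce loneliness and its implications among older adults". The Objectives section, however, gives self-compassion a separate, earlier objective.

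**The concern.** The hypotheses concern 30 days. A group-by-time test over four occasions asks something else: whether the two mean profiles differ in shape anywhere from baseline to the second month. By the second month both groups have been trained. Controls catching up between weeks 4 and 8 could then contribute to a significant result, or dilute the overall contrast if the early difference is modest. Either way, the result would not say whether trained participants were better off than untreated ones at 30 days.

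In addition, the 90% is attached to no outcome. A reader cannot tell what the power refers to, or which of the five 30-day results carries the efficacy conclusion.

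**Working it through.** **1. The plan's own figure.** Inputs from the sample size section: f = 0.2, alpha 0.05, power 90%, 2 groups, 4 times. Assumed, because not stated: within-person correlation 0.5 and sphericity. For the group-by-time interaction:

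- noncentrality = f² × N × 4 / (1 − 0.5) = 0.04 × 46 × 4 / 0.5 = 14.72
- degrees of freedom = 3 and (46 − 2) × 3 = 132
- power = 0.903

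So 46 reproduces. At correlation 0.3 the test needs 64, and at 0.7 it needs 28. A between-group main-effect test at correlation 0.5 would need 168. The stated figure is therefore the four-time interaction test, and its arithmetic is sound.

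**2. What each time compares**, as described in the procedures section:

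| Time in the ANOVA | Intervention group | Control group |
|---|---|---|
| Baseline | measured | measured, untrained |
| Right after intervention | measured | no concurrent measurement described |
| One month (week 4) | measured | measured, still untrained |
| Second month (week 8) | measured | measured, four weeks after own training |

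Week 4 is the only time after baseline with a described untreated comparator. It is also the time named in the hypotheses.

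**3. Detectable week-4 difference.** Two equal groups, two-sided 0.05, 90% power, adjusted for baseline at correlation r (assumed), with d in SD units of the outcome. The normal approximation is d ≈ (1.960 + 1.282) × 2 × √(1 − r²) / √N.

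- N = 100, r = 0.5: 3.242 × 2 × 0.866 / 10 = 0.56
- N = 76, r = 0.5: 3.242 × 2 × 0.866 / 8.718 = 0.64

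The noncentral t with N − 3 degrees of freedom gives:

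| Analysed | r = 0.3 | r = 0.5 | r = 0.7 |
|---|---|---|---|
| 100 | 0.63 | 0.57 | 0.47 |
| 76 | 0.72 | 0.65 | 0.54 |

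The plan states no retention rate. The 76 reads its allowance as 46 analysed of 60 enrolled: 100 × 46/60 = 76.7.

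**4. Comparison with the planned effect.** With two groups and two times (baseline and week 4), a between-group difference in change of D gives interaction components of D/4 in each cell, so f = D / (4 SD). Then f = 0.2 means D = 0.8 SD. At within-person correlation 0.5 the SD of change equals the SD of a single measurement, so 0.8 holds on either scale. Every entry in the table is below 0.8. At d = 0.8 and r from 0.3 to 0.7, week-4 power is 95% or more with 76 analysed and at least 98.6% with 100.

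**5. Five outcomes.** Suppose each were tested at 0.05 and any one significant result were read as efficacy; the plan does not say this. The chance of at least one false positive is 1 − 0.95⁵ = 22.6% if the outcomes are independent, 18.3% at between-outcome correlation 0.5 and 12.7% at 0.8 (correlations assumed).

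**The case against.** The strongest reply is that this is a feasibility pilot. Efficacy is its second, preliminary aim, and the ANOVA appears only as a sizing device. No sentence says efficacy will be concluded from that omnibus test. The hypotheses already fix 30 days, and the week-4 untreated data are already collected. This stands as a limit on the force of the point. It does not remove the point, because the plan sets directional efficacy hypotheses and sizes itself at 90% power for a test that does not address them.

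A reader might infer that the plan carries a false-positive rate of 13 to 23%. The documents do not support that. They state no rule that one significant result out of five shows efficacy, and they claim no familywise rate. Those figures are conditional only.

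A reader might also infer that the trial is underpowered or that 46 was miscalculated. Neither holds: the 46 reproduces, and the week-4 comparison at the revised size is well powered for the planned effect.

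Nor can it be said that no ranking of outcomes exists. The text leans towards loneliness, and the separate protocol, the schedule of assessments and the questionnaires are not visible and may rank the outcomes.

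Finally, the Compensation section's extra control follow-up raises the possibility that the controls' later times run on their own clock. If so, the post-baseline times in the ANOVA would not be concurrent between groups, and the later ones would compare trained with trained. That would not rescue the four-time test, but it shows that the control schedule needs reconciling.

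**Conclusion.** The point holds as a mismatch between the powered test and the hypothesis. The four-time interaction includes one time without an untreated comparator and one without a described concurrent control measurement, so it does not isolate the 30-day effect. The consequence is moderate to small. No shortfall in power appears at the planned effect, and the feasibility and acceptability conclusions are untouched. What is gained is an interpretable main contrast whose stated power belongs to it.

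The missing lead outcome is the weaker half. It matters for how efficacy results are selected and reported, and a ranking in an unseen attachment would settle it. The mismatch in the tested contrast would remain in the visible text even then. The detectable differences rest on assumed baseline correlations of 0.3 to 0.7 and on the reading of attrition given above.

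**What to change.** Before any between-group data are examined:

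- Make the main efficacy analysis the week-4 difference between groups, adjusted for the baseline value, two-sided 0.05, for one named outcome. Loneliness is suggested by the population, Purpose and outcome text. The investigator should confirm it, because the Objectives section gives self-compassion its own earlier objective.
- Report the other four outcomes as exploratory week-4 differences with 95% confidence intervals.
- Report results right after the intervention as change within the intervention group, unless a concurrent control measurement exists. Report week 8 descriptively, noting that controls have been trained by then.
- Reconcile the control visit timing between the procedures and Compensation sections.
- Replace the four-time power statement with one for the week-4 comparison at the revised sample size, stating the assumed baseline correlation and attrition.

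The cost is a short paragraph and one power calculation, with no change to visits or data. The downsides are that week-8 data leave the main test and four outcomes become exploratory.

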Except for demographic information, other data and some intervention evaluation questions will also be collected at the end of the intervention, at 4 week and 8 week. There will be one extra data collection for control group before they get their intervention at 4 week. If for any reason participants refuse to participate during any part of the study, we will collect the reasons for their premature dropping out of the study. Some of the questions that will be asked to those who drop out of the study prematurely are in "Guide for Quantitative Data Collection" attachment.

The intervention primarily involves orientation and mindfulness practices such as proper posture, breathing techniques. We will also teach them the importance of the intervention and daily

practices, how to deal with thoughts that may arise during the meditation practice, and encourage them to write about their daily meditation experiences in the diary provided to them. We will also teach them loving-kindness meditation and provide them with guided meditation on an MP3 device, which they do not have return upon completion of the study. The orientation and intervention will happen in the lobby area, common space, or OLLI classroom in a group setting. The LKM recording will consist of mindfulness practice where they are guided to focus on compassion and kindness for themselves and others. Recording for both brief orientation and LKM are attached. After intervention session is over, participants are encouraged to practice guided meditation daily using the mp3 device for 20-25 minutes on their own at time appropriate for them. They will be encouraged to write their experience in the diary after the practice, which can take from 5 to 10 minutes daily. The diary will be a small folder with some questions to guide their entries daily. Please see dairy or journal requirement attachment for more information. The diary will be given to the participants after the intervention training. There will be weekly reminders via phone call to practice meditation daily and write their experiences in the diary. Weekly call will be around 5-10 minutes weekly for four weeks.

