**What is the anticipated time commitment involved for each study procedure (e.g. 30 minutes for the survey, 1 hour for the interview, etc.)? What is the total time that each participant will spend in the entire study?**

---

*Describe the duration of study participation (i.e. the anticipated amount of time commitment required for each subject), the length and number of study visits, and the timetable for study completion.*

*Describe, in timeline sequence, the activities participants will be asked to perform specifically for the research, and how much time each activity will take. Attach your schedule of assessment, if applicable.*

Each session with participants will take about 30-60 minutes. Please see attached schedule of assessments for a detailed anticipated amount of time commitment.

The total time that each participant will spend in the entire study would be around 300 minutes. The focus group will have additional 90 minutes.

Baseline data collection: 60 minutes

Orientation and intervention and data collection: 60-90 minutes

Post intervention data collection at 4 week: 30 minutes

Time 2 control group data collection: 30 minutes

Follow-up data collection at 8 week: 30 minutes

Daily meditation practice: 20-25 minutes

Daily journal entry: 5-10 minutes.

Weekly call: about 5 -10 minutes

Focus group interview: 90 minutes (2 different groups)

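### Does the 300-minute total for study participation need correcting because it cannot contain the daily home practice?

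*Combined protocol and SAP*

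**What the plan says.** The time-commitment question under *Research Methods* asks how long each procedure takes and how long each participant spends in the study overall. The answer opens with a typical session length, "Each session with participants will take about 30-60 minutes", and refers to an attached schedule of assessments for detail. It then gives the total: "The total time that each participant will spend in the entire study would be around 300 minutes". Focus-group members have a further 90 minutes.

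An itemised list follows:

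- baseline: 60 minutes
- training session: "Orientation and intervention and data collection: 60-90 minutes"
- 30 minutes each for the 4-week visit, the control group's Time 2 visit and the 8-week visit
- "Daily meditation practice: 20-25 minutes"
- "Daily journal entry: 5-10 minutes"
- a weekly call of 5 to 10 minutes

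The length of the home period comes from *How will you conduct this study?*. There, "participants are encouraged to practice guided meditation daily using the mp3 device for 20-25 minutes on their own", and "Weekly call will be around 5-10 minutes weekly for four weeks". Of the 4-week visit it says: "At this data collection session, we will also collect 30-day journal folders".

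**The concern.** The form asks for total time in the whole study, and the answer excludes only the focus group. The natural reading is that everything else on the list is inside the 300 minutes. The two daily items alone exceed 300 minutes after 9 to 12 days (300/35 = 8.6; 300/25 = 12), before any visit is counted, and the home period lasts 28 to 30 days.

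This is a figure on participant burden given to an ethics board in a required field. If it omits most of the time, the board could underestimate what is being asked of adults aged 50 and over. The diary is also not purely optional from the study's side: *Compensation* pays $30 for the post-intervention visit with the diary, and $20 if no diary was kept. A second apparent mismatch is that the typical session length of up to 60 minutes does not cover a training session of up to 90.

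**Working it through.** **Inputs.** All durations are from the time-commitment answer. The four weekly calls and the 28- or 30-day home period are from *How will you conduct this study?*.

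**Can 300 be reproduced?** Three readings were tried.

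1. Visits only.
   - Intervention arm: 60 + (60 to 90) + 30 + 30 = 180-210.
   - Controls, if Time 2 takes the place of one of the other 30-minute visits: also 180-210.
   - Controls, if Time 2 is an added visit: 210-240.
2. Visits plus calls. Calls are 4 × (5 to 10) = 20-40.
   - Intervention arm: 200-250.
   - Controls: 200-250, or 230-280 with the added visit.
3. Every listed item counted once, without the focus group.
   - Low: 60 + 60 + 30 + 30 + 30 + 20 + 5 + 5 = 240.
   - High: 60 + 90 + 30 + 30 + 30 + 25 + 10 + 10 = 285.

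None gives exactly 300. The second and third readings come close at their upper ends (280 and 285), and the figure is stated as approximate.

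**Home time.** Practice plus diary is (20 + 5) to (25 + 10) = 25-35 minutes a day.

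- 28 days: 28 × 25 = 700 to 28 × 35 = 980.
- 30 days: 30 × 25 = 750 to 30 × 35 = 1,050.

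**Totals if practice is done every day (minutes).**

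| | Contact | 28 days | 30 days |
|---|---|---|---|
| Intervention; controls without an added visit | 200-250 | 900-1,230 | 950-1,300 |
| Controls with an added visit | 230-280 | 930-1,260 | 980-1,330 |

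Relative to 300: 900/300 = 3.0 up to 1,330/300 = 4.4.

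**Lower adherence.** Practice is encouraged, not required, so full adherence is an assumption. At half adherence the total runs from 14 × 25 + 200 = 550 to 15 × 35 + 250 = 775, or 805 with 280 minutes of contact.

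**How much home time fits inside 300?**

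- Most: (300 − 200)/25 = 4.0 days.
- Least: (300 − 280)/35 = 0.6 days.

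So the total can hold contact time and at most about four days of practice.

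**Session length.** *How will you conduct this study?* splits the training session into orientation (10-20), recorded training (30-35) and questions (10-20), which sum to 50-75 minutes. Participants then complete questionnaires on their own. The 60-90 minute item includes that data collection, and the 30-60 minute figure is stated as approximate.

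**Where is 300 used?** Nowhere else in the document. The sample-size paragraph rests on an effect size, alpha, power and a flat attrition percentage. The efficacy outcomes are questionnaire scores. Adherence, listed under acceptability, would naturally be judged against the daily practice target and the diary, which asks how long the participant meditated that day.

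**The case for a change.** The strongest case for acting is that the field asks about the entire study, one item is expressly excluded, and nothing says that home practice is excluded too. The total fits only near-complete non-adherence, which cannot be what the investigator anticipates. A reader who adds up the items must take the duration from another section and then contradicts the stated figure. Relabelling would cost one sentence.

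Most of this stands. The total is unlabelled, and as an all-inclusive figure it is wrong by a wide margin even at half adherence. Three things limit its weight. First, the sentence directly before it concerns sessions, and contact time reaches 280 minutes, so a rounded contact-time figure is a credible reading. Second, the per-day times follow a few lines below, so an ethics reader had the home load in view. Third, the schedule of assessments, to which the answer defers for detail, and the consent form are not in the available text. Whether participants were given an incomplete figure cannot be judged, and no error can be inferred from their absence.

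The session-length mismatch is trivial. Whether controls have a further one-month follow-up, which *Compensation* pays for but the procedures do not clearly describe, is a separate question of visit schedule. It moves the total by only 30 minutes.

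**Conclusion.** The observation is correct but calls for no change to the plan. The 300-minute figure cannot contain 700-1,050 minutes of daily practice and diary. It is best read as approximate contact time, for which the listed items give 200-250 minutes in the intervention arm and 200-280 among controls. That reading is an inference: the document does not say how 300 was reached. The full-practice totals of about 900-1,300 minutes (intervention) and 900-1,330 (controls) assume practice on every one of 28 to 30 days.

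The slip is clerical and lies in an application field. Relabelling the total would leave allocation, visits, home practice, outcomes, sample size and analysis as they are, and no result of the trial would be read differently.
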